**Aims 2-4** will use 14 years (2004-2017) of enrollment and benefits data, insurance claims, standardized cost data, geocoded census data, and credit report SES variables from a large U.S. commercial health plan obtained through Optum. We will have detailed benefit information for ~80% of employer groups obtaining coverage from the health plan. For employers with missing deductible levels, we have developed an imputation algorithm that has 97.0% sensitivity and 96.2% specificity (MD-2). The health plan links insurance claims to de-identified credit report data, including novel indicators of individual-level SES (household income and net worth) and imputed information on ethnicity based on member surname (MD-2, see 'Methods to monitor and address missing data', below). Data from this insurer have been used in published health services research studies and the study team has experience examining a range of health care outcomes using these data. The research team's extensive experience using these data will enable us to efficiently create analytic cohorts and study variables, building upon previously developed methods. We will leverage existing health plan data from 2004-2014 that the study team has used in other projects, and add data through 2017 in December 2017 (see Optum letters).

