### **Study Population (PC-2)** (See section D below for further detail)

The **Aim 1** study population will consist of adults with asthma and parents of children with asthma. Eligible participants will be those who are currently enrolled in employer-sponsored and non-group health insurance plans (high-deductible plans with and without a PDL, or traditional plans). Participants will be drawn from two different populations. First, we will recruit members of a health plan in order to ensure representation of patients through their membership in HSA-HDHPs with and without PDLs. Second, we will recruit additional patients with asthma and their caregivers through AAFA in order to ensure representation of patients who have other health insurance carriers.

The health plan population will be identified through enrollment and claims data from HPHC among non-group plans and large national employer accounts. HPHC offers HSA-HDHPs with the same standardized, federally mandated benefits as the national health plan used in Aims 2-4, as well as a PDL containing similar medications, including asthma controller and rescue medications. Eligible patients will include adults aged 18-64 with a diagnosis of asthma and/or a child with asthma. Using methods from our previous asthma studies, an asthma diagnosis will be defined as having at least one inpatient, ED, or outpatient claim in the prior year with a diagnosis of asthma based on the following International Classification of Diseases, 9th edition (ICD-9) codes (up through 2015): 493.XX and ICD-10 codes (2015 and after): J45.2x, J45.3x, J45.4x, J45.5x, J45.90x, J45.990, J45.991, J45.998. We will select patients who have been enrolled in an employer-sponsored or non-group market HSA-HDHP with or without a PDL, or a traditional plan without a high deductible, for the prior year. We will identify other family members with asthma sharing the same insurance plan. Among those eligible in each sub-group outlined in Table 1 below, we will randomly select up to 140 from each cell to send a recruitment mailing/email, for a total of up to 660 patients or parents invited to participate.

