Thus, to be included in the study, all subjects will have at least 12 months in both the Pre and Post periods. We selected a follow-up period of up to three years because we hypothesized that patients in HSA-HDHPs with PDLs might experience benefits that take longer than one year to manifest. A primary purpose of the pre period is to ensure precise matching between groups on both the level and trend in key baseline characteristics (e.g., employer characteristics, demographics, utilization patterns, etc.). Our difference-in-difference analyses will include annual-to-annual comparisons (baseline to follow-up year 1, baseline to follow-up year 2, etc.). This will allow intuitive comparisons such as "relative to controls, adherence among HSA-HDHP members with PDLs increased by 4% in follow-up year 1 compared to baseline, but by follow-up year 2, adherence had increased by 11% compared to baseline." We have used this approach in a variety of studies and find that it translates well to clinical and policy audiences. For analyses of outcomes in the second and third year post-switch, we will only include study group patients and their matched controls who have had that length of follow up. We will compare and report differences in baseline characteristics for the subgroups of study cohort members that remain enrolled for each additional year.

We will exclude those over age 64 who are eligible for Medicare. We will identify members with asthma during a 12-24-month period prior to the index date using the same claims-based algorithm used to identify HPHC members with asthma for the Aim 1 interviews, with the inclusion of ICD-9 codes 493.XX to identify a diagnosis of asthma through October 2015. This broad definition will include patients with *intermittent asthma* as well as those with *persistent asthma*, for whom controller medications are recommended. Subgroup analyses will focus on the subset of patients who meet the HEDIS definition of persistent asthma ( $\geq 1$  ED or inpatient visit with asthma as the principal diagnosis,  $\geq 4$  outpatient visits with any asthma diagnosis, or  $\geq 4$  asthma drug dispensing events in the baseline year).

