2. **Use of asthma rescue medications (Aims 2-3):** We will assess use of albuterol and levalbuterol inhalers, the primary asthma rescue medications prescribed to patients, which are subject to the deductible in HSA-HDHPs without PDLs, free in HDHPs with PDLs, and subject to copayments in traditional plans. All albuterol and levalbuterol inhalers are brand-name drugs containing 200 puffs each. We will exclude nebulized versions as these are predominantly used by younger children and do not come in standardized doses. As in our prior study, we will measure the standardized number of inhalers dispensed per month based on National Drug Code (NDC) in pharmacy claims. Given the inter-relationship between rescue and controller medication use, we will also measure the ratio of controller medications to total asthma medications, a metric for which higher values are associated with better asthma control and lower rates of asthma-related ED visits.
3. **Use of spacers and nebulizer machines (Aims 2-4):** Based on input from patients and stakeholders, and with additional input from questions from added questions in the qualitative interview guide in response, we will assess changes in the number of spacers and nebulizer machines received by study patients, based on claims data. We will measure changes in receipt of spacers and nebulizer machines after a switch to an HSA-HDHP vs. remaining in a traditional plan to see if changes in the cost-sharing for these devices leads to a decrease in receipt and an increase in OOP costs to families.
4. **Asthma-related ED visits and hospitalizations (Aims 2-3):** As a measure of potentially avoidable short-term complications, we will measure asthma-related ED visits and hospitalizations that have a primary ICD-10 diagnosis code for asthma.
5. **OOP health care costs (Aim 4):** We will calculate consumer price index (CPI)-adjusted OOP costs for asthma medications and other health services, summing deductible, co-pay, and coinsurance amounts, aggregated into annual measures. Financial burden due to OOP costs will be defined as annual family OOP costs as a percent of family income, with cutpoints of >5% and >10% to indicate financially burdensome OOP costs.

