For analyses of rescue medication use, we will focus on albuterol and levalbuterol inhaler users. We will limit the time period of interest to 2009-2017, as albuterol inhalers, the primary asthma rescue medication, became available only as higher-priced branded CFC-free medications as of 2009 due to the FDA ban on generic CFC-containing inhalers. The standardized number of rescue inhalers dispensed will be modeled as count data in difference-in-differences models. ITS models will be used to model changes in level and trend of monthly rates of rescue inhalers dispensed, as in our previous study. Because use of controller medications can affect need for rescue medications, we will add controller medication adherence as a co-variate; sub-analyses will stratify by controller medication use in the baseline period. We will also model the ratio of controller medications to total asthma medications. For analyses of asthma-related ED visits and hospitalizations, outcomes can be binary, counts, or continuous. We will use logistic GEE models to estimate the effect of switching to each type of HSA-HDHP on binary outcomes such as any asthma-related hospitalization. We will use negative binomial regression to model the effect for count outcomes such as ED visits. We will select the conditional mean and variance functions based on the actual data, using a log link with a Gamma error distribution. To inform final model specification, we will employ specification tests including the Pregibon Link test for non-linearity and a modified Park test to select the conditional variance function.

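### The asthma ED-visit and hospitalization outcome names only ICD-10 codes, so as written it has no baseline events for any year-3 comparison and for nearly all year-2 index months; the ACG scores carry the same wording.

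*Combined protocol and SAP*

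**What the plan says.** - **Outcome.** Outcomes, item 4, measures "asthma-related ED visits and hospitalizations that have a primary ICD-10 diagnosis code for asthma". No ICD-9 code is named. The section calls the listed measures the primary outcomes for Aims 2-4, and Sample Size and Power treats this one as one of three primary outcomes (Table 3, baseline 8.4 per 100).
- **Data.** Sources of Data states that Aims 2-4 "will use 14 years (2004-2017) of enrollment and benefits data, insurance claims".
- **Cohort.** Study Population uses "ICD-9 codes 493.XX to identify a diagnosis of asthma through October 2015" for the Aims 2-4 cohort. The Aim 1 text of the same section gives both code sets with year-level dates: "codes (up through 2015): 493.XX and ICD-10 codes (2015 and after".
- **Persistent asthma.** The HEDIS definition in Study Population includes an "ED or inpatient visit with asthma as the principal diagnosis", with no code set attached.
- **Contrasts.** Study Population: "Our difference-in-difference analyses will include annual-to-annual comparisons (baseline to follow-up year 1, baseline to follow-up year 2, etc". For years 2 and 3, "we will only include study group patients and their matched controls who have had that length of follow up".
- **Calendar limits.** The Analysis plan sets one for rescue inhalers ("We will limit the time period of interest to 2009-2017, as albuterol inhalers") and none for ED visits and hospitalizations.
- **ACG scores.** Predictors and Covariates says that they are calculated from ICD-10 codes in the baseline period and names no ICD-9 codes. Table 2 lists ACG as a predictor, a matching variable and a stratifier. The family mean and the employer median also enter the matching.

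**The concern.** Each follow-up year is compared with the year before the index date. If the event definition recognises only ICD-10, events before the changeover are invisible, and most baselines fall there. With no baseline events in either arm, the planned logistic and negative binomial models have no baseline level from which to estimate a change.

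Follow-up of up to three years was chosen because benefits might take more than a year to appear. The longest comparison is the one that fails completely. Overview of Study Protocol, Study Population, and Generalizability and Limitations also rely on matching on baseline trend. For this outcome there would mostly be no trend to match.

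The ACG wording reaches further. Read in the same way, scores for most baselines would have no usable diagnosis codes. They feed the employer-level and individual-level matching, and the Analysis plan puts key Table 2 predictors into all models. On that reading the matched cohorts and adjusted models for adherence, rescue use and out-of-pocket costs would also be touched.

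**Working it through.** The plan states no share of covered months, so there is no figure of its own to reproduce.

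**Inputs**
- Claims January 2004 to December 2017: 14 × 12 = 168 months (Sources of Data; the end of 2017 is the most generous reading).
- Baseline of 12 months and follow-up of up to 36 months (Overview of Study Protocol).
- Year-k analyses include only patients with k full years of follow-up (Study Population).
- Changeover in October 2015 for the Aims 2-4 cohort, with January 2015 and January 2016 as the extremes of the Aim 1 wording.
- Assumption, implied by Study Population but not stated: claims before the changeover carry ICD-9 codes only.

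**Step 1. Months without ICD-10.** Share = months before the changeover / 168.

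| ICD-10 starts | Months without ICD-10 | Share |
|---|---|---|
| 1 Jan 2015 | 132 | 78.6% |
| 1 Oct 2015 | 11 × 12 + 9 = 141 | 83.9% |
| 1 Nov 2015 | 142 | 84.5% |
| 1 Jan 2016 | 144 | 85.7% |

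**Step 2. Possible index months.** Number the months 0 (January 2004) to 167 (December 2017). Index month i needs i ≥ 12 for a full baseline and i + 12k − 1 ≤ 167 for k years of follow-up, so i runs from 12 to 168 − 12k.
- Year 1: 12 to 156, which is 145 months (last index January 2017).
- Year 2: 12 to 144, which is 133 months (last index January 2016).
- Year 3: 12 to 132, which is 121 months (last index January 2015).

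**Step 3. Baseline status.** Let c be the first ICD-10 month (October 2015 is c = 141). The baseline covers i − 12 to i − 1. It is zero if i ≤ c, fully ICD-10 if i ≥ c + 12, and mixed otherwise.

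| Comparison | Index months | Zero | Mixed | Fully ICD-10 |
|---|---|---|---|---|
| Year 1 | 145 | 130 (89.7%) | 11 | 4 |
| Year 2 | 133 | 130 (97.7%) | 3 | 0 |
| Year 3 | 121 | 121 (100%) | 0 | 0 |

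With ICD-10 from 1 November 2015 the rows become 131/11/3, 131/2/0 and 121/0/0.

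**Step 4. Sensitivity to the date wording.** With c = January 2015: 121/11/13, 121/11/1 and 121/0/0. With c = January 2016: 133/11/1, 133/0/0 and 121/0/0. The year-3 result is the same throughout, because the last year-3 baseline ends in December 2014.

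**Step 5. Consequence for the estimate.** On the ratio scale of the planned models, the effect is (follow-up / baseline) in the intervention arm divided by (follow-up / baseline) in the control arm. With both baselines zero, each inner ratio divides by zero and the effect is undefined. This covers the whole of year 3. For year 2, only 3 of 133 index months could supply any baseline event, and none has a full baseline.

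**The case against.** The best reply is that this is shorthand and that nobody would run it literally. The evidence for that is good: the same cohort is built with 493.XX, the HEDIS definition describes almost the same event with no code-set limit, and Table 3 assumes a baseline of 8.4 per 100. The recurrence of ICD-10 alone in the ACG sentence also suggests loose usage. I accept that a slip is the likely explanation. But the definition of a primary outcome should not depend on an unwritten correction, and no section supplies one. The recurrence is a reason to correct both places, not to leave both.

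Other points on that side:
- **Matched controls.** A reader might infer that the estimate is biased in one direction. The documents do not support this. Controls take the index dates of their matched intervention patients, so the same gap falls on both arms. Shared dates do not create baseline events, however.
- **Calendar months.** A reader might take 84% as a share of patients, events or power. It is not, and those shares cannot be given because the distribution of index dates is not stated. Year 1 is also less affected: 15 of 145 index months (10%) have at least some ICD-10 baseline. The year-3 result needs no such distribution.
- **Dropping year 3.** Generalizability and Limitations allows follow-up to be cut to two years if dropout is substantial. That would not rescue the outcome, since year 2 is nearly as bare.
- **Dates.** The two changeover wordings are coarse against fine more than contradictory. Aligning them is tidying, but the outcome rule needs one exact date.

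**Conclusion.** The point holds as a gap in a stated rule that should be fixed. Followed as written, item 4 gives no events in 141 of 168 calendar months (79% to 86% across the date wordings) and no estimable baseline-to-follow-up contrast for year 3 or for nearly all of year 2. This rests on pre-changeover claims carrying ICD-9 only and on data ending in December 2017.

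It does not show that the study would in fact be run this way, that results would lean towards either arm, or how much power would be lost. Nor can the rest of the plan be called untouched: the ACG sentence has the same defect on the same reading. The general ED, hospital and outpatient visit counts used in matching are not tied to a diagnosis code and are not affected by item 4.

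**What to change.** 1. In Outcomes, item 4, define the event by a primary diagnosis of ICD-9 493.XX for service dates before the changeover, and of the J45 codes already listed in Study Population from the changeover on.
2. In Predictors and Covariates, state that ACG scores use the code set in force on the service date.
3. State one changeover date and use it in both places in Study Population and in Outcomes.

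The cost is two sentences and one aligned date. The codes are already in the plan, no new data are needed, and Table 3 is unchanged. With both code sets, all 168 months are covered and all 121 possible year-3 index months have a measurable baseline, instead of none.

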## **Predictors and Covariates**

Table 2 shows the main predictors and covariates we will use in the proposed study for propensity matching to create study cohorts (CI-1, 4-5), predicting or adjusting outcomes, or stratifying analyses. Our primary predictor variables include study period and insurance type. Study period indicates the one-year period before or up to three years after the index date. Insurance type includes: 1) HSA-HDHP without PDL; 2), HSA-HDHP with PDL; and 3) traditional plan.

Other co-variates include asthma severity in the baseline period using the HEDIS definition for persistent asthma (see above under Study Population), and using chronic oral corticosteroid therapy (180+ days in the prior year) or any use of omalizumab in the baseline year to define severe asthma. To estimate co-morbidity, we will use the well-established Johns Hopkins Adjusted Clinical Groups (ACG) scores which use ICD-10 codes in the baseline period to calculate a standardized morbidity score in a specified time period. We will measure the presence of other chronic conditions from claims data in the baseline year using the Johns Hopkins ACG system. We will also measure whether enrollees have COPD as a co-morbidity, as there can be overlap with COPD and asthma, and use of similar medications.

A unique innovation of our study is the availability of data linkages (IR-2) with consumer data from a

major credit reporting company linked to insurance claims from our data vendor, Optum. Consumer data elements include total household income, net

worth, and race/ethnicity. We will combine self-reported race/ethnicity data from credit card and loan applications with data from Optum on surname analysis for identifying Hispanic or Asian ethnic groups and geocoding to derive race/ethnicity from census data. We will also use census-based indicators for neighborhood education and poverty levels. Other variables used to propensity-match cohorts and adjust for confounding will include sex and age; state/region of residence; individual versus family plan; baseline number of outpatient visits, presence of an inpatient hospitalization, and total expenditures; employer size (number of employees); and average employer baseline expenditures per capita (CI-1, 4-5).

Using methods from our prior family-level studies, we will aggregate individual member data to create family-level co-variates that will be applied to each subject and used for individual-level propensity matching and analyses. Patients with individual coverage will be considered a family of one. Family-level variables include: number of family members; mean age of children in the family; mean age of adults; baseline mean family ACG score; number of family members with asthma; and number of asthma and other medications used by the family, and number of ED visits and hospitalizations in the baseline year.

Our study population includes health plan members working for employers that either switched to an HSA-HDHP without PDL or HSA-HDHP with PDL, or remained in a traditional plan or an HSA-HDHP without PDL, respectively, for all employees. While this minimizes member-level selection, employer-level selection could still bias results. We will therefore use a validated and rigorous employer- and individual-level propensity score classification/matching approach (CI-1, 4-5) that is superior to a single-level matching technique. For employer-level propensity matching, potential predictors of an employer HSA-HDHP switch in our propensity score models will include employer size

